4.3 Medical history

Medical history and ongoing conditions, including cancer-related conditions and symptoms entered on (e)CRF will be summarized by treatment group. Separate summaries will be presented for ongoing and historical medical conditions. The summaries will be presented by primary system organ class (SOC), preferred term (PT) and treatment group. Medical history and current medical conditions will be coded using the Medical Dictionary for Regulatory Activities (MedDRA) terminology. The MedDRA version used for reporting will be specified as a footnote in the applicable tables/listings.

4.4 Concomitant medications with specific impact on the analysis

Patients who take additional anti-neoplastic therapy before discontinuing study treatment (i.e., anti-neoplastic therapy other than study treatment) will be identified as protocol deviations.

4.5 Patient disposition

Enrollment by country and center will be summarized by treatment group using the FAS. The number of screened patients and the reason for screening failure will be displayed.

The following summaries will be provided:

- Number (%) of patients who were randomized (based on data from IRT system)
- Number (%) of patients who were randomized but not treated with Midostaurin/Placebo
- Primary reason for not being treated (based on ‘End of Treatment Phase Completion’ eCRF page)
- **Treatment phase: Induction, consolidation and post-consolidation**
 - Number (%) of patients who were treated (based on exposure eCRF pages of each study treatment component completed with non-zero dose administered).
 - Number (%) of patients who are still on-treatment
 - Number (%) of patients who discontinued the study treatment
 - Number (%) of patients who entered consolidation, post-consolidation phase
 - Number (%) of patients who completed each treatment phase: induction, consolidation and post-consolidation treatment phases as per protocol.
 - Primary reason for study treatment discontinuation for each treatment phase (induction, consolidation, post-consolidation)
- **Post-treatment follow-up phase**
 - Number (%) of patients who have entered the post-treatment follow-up
 - Number (%) of patients who have discontinued from the post-treatment follow-up
 - Reasons for discontinuation from the post-treatment follow-up
- **Survival follow-up phase**
 - Number (%) of patients who have entered the survival follow-up
 - Number (%) of patients who have discontinued from the post-treatment follow-up
 - Reasons for discontinuation from the post-treatment follow-up

5 Protocol deviations

The number (%) of patients in the FAS with any protocol deviation will be tabulated by deviation category. All protocol deviations will be listed.

6 Treatments (study treatment, rescue medication, concomitant therapies, compliance)

6.1 Study treatment / compliance

Duration of exposure, actual cumulative dose, dose intensity (DI) and relative dose intensity (RDI) will be summarized by treatment group, separately for each component of study treatment. The duration of exposure will also be presented for the study treatment. Duration of exposure will be categorized into time intervals; frequency counts and percentages will be presented for the number of patients in each interval (0 to \leq 4 weeks, 4 to \leq 8 weeks, 8 to \leq 12 weeks, 12 to \leq 24 weeks, 24 to \leq 48 weeks, > 48 weeks). The number (%) of patients, who have dose reductions or interruptions, and the reasons, will be summarized by treatment group.

Patient level listings of all doses administered on treatment along with dose change reasons will be produced. The safety set will be used for all summaries and listings of study treatment.

6.2 Cycle definition

Cycle length will be calculated from the cycles recorded in the visit panel. Each cycle ends the day before the next cycle starts.

Cycle length= (date of Day 1 of the next cycle – date of Day 1 of the current cycle).

The length of last cycle (last date of last intake to the study component) – (date of Day 1 of the last cycle).

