4.2.2 Consolidation phase

Patients achieving CR or CRi with adequate blood count recovery after induction with one or two cycles of induction therapy will proceed to consolidation therapy with either 3 or 4 cycles of intermediate-dose cytarabine respectively, or to HSCT with or without preceding consolidation cycles. Patients may undergo transplantation at the discretion of the Investigator (refer to 2017 ELN and 2016 National Comprehensive Cancer Network (NCCN) recommendations). In patients who are treated with allogeneic HSCT instead of consolidation therapy or after start of consolidation therapy the conditioning regimen and management after transplantation will be according to local institutional standards. Study treatment will be interrupted at least 48 hours before the initiation of the transplant conditioning regimen. Patients with transplantation and recovery from the procedure will not receive further cycles of consolidation treatment but receive post-consolidation treatment with study drug. They can start the post-consolidation therapy not earlier than 30 days after transplant but not later than 100 days after transplant.

Patients will receive midostaurin (two 25 mg capsules) or placebo (2 capsules) twice daily orally from day 4 until 48 hours prior to the start of the next consolidation cycle.

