6.3 Duration of exposure to Midostaurin/placebo

Duration of exposure to a study component (days) = (last date of last intake to the study component) – (date of first administration of the study component) + 1;

6.4 Duration of exposure to cytarabine, daunorubicin or Idarubicin in induction and consolidation treatment phases

For each treatment cycle, duration of exposure to the study treatment components (days) = (last date of last intake to the study component) – (date of first administration of the study component) + 1;

Therefore, the total duration of exposure will be the sum of exposures for each treatment cycles in induction and consolidation.

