6.7.1 Planned cycles lengths

A cycle length is planned to be 28 days for all patients who reached CR, CRi with adequate blood count recovery, PR or No response at end of each cycle. If the patient has CRi without adequate blood count recovery, the planned cycle length might be prolonged to:

- Up 42 days for induction cycle 1
- Up 49 days for induction cycle 2
- Up 49 days for all consolidation and post-consolidation treatment cycles.

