6.7.2 Dose Intensity (DI) by cycle analysis

6.7.2.1 Midostaurin/Placebo

For cycles except last cycle or last cycle with length as scheduled or longer

- DI_c [mg/day] = (Total actual dose in an actual cycle [mg]) / actual cycle length [days]

For all cycles

- RDI_c [%] = DI_c [mg/day] / Planned Dose Intensity [mg/day] * 100

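### For transplanted patients who resume study drug, the SAP's cycle-length rule counts the protocol-permitted drug-free HSCT interval in the dose-intensity denominators, so reported RDI falls without any missed dose

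*SAP*

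**What the plan says.** SAP 6.2 states that "Each cycle ends the day before the next cycle starts" and gives the rule as "Cycle length= (date of Day 1 of the next cycle – date of Day 1 of the current cycle"). Only the final cycle differs: it ends at the last intake of the component. SAP 6.7.2.1 defines dose intensity (DI) by cycle as "Total actual dose in an actual cycle [mg]) / actual cycle length [days"], and 6.7.3.1 divides cumulative dose by the sum of the same lengths. RDI is DI over planned dose intensity (PDI), for which no mg/day value is given. SAP 6.7.2.2 and 6.7.3.2 apply the same rules to chemotherapy.

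On planned length, SAP 6.7.1 says "A cycle length is planned to be 28 days for all patients who reached CR, CRi with adequate blood count recovery". It extends this to 42 days (Induction 1) or 49 days (later cycles) only for CRi without adequate recovery. HSCT is not mentioned.

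Midostaurin/placebo duration (SAP 6.3) and study-treatment duration (6.5) are last date minus first date plus 1. Chemotherapy duration (6.4) is summed cycle by cycle.

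Protocol 4.2.2 stops study treatment at least 48 hours before conditioning, rules out further consolidation after transplant, and says of these patients: "They can start the post-consolidation therapy not earlier than 30 days after transplant but not later than 100 days after transplant". Protocol 6.3.1 exempts HSCT from the 28-day limit on interruptions.

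**The concern.** The cycle that follows HSCT is post-consolidation cycle 1. Under SAP 6.2 the last pre-HSCT cycle therefore runs on through conditioning, transplant and the wait afterwards. The numerator holds one cycle of drug, while the denominator holds that cycle plus one to three and a half months in which the protocol has the patient off drug. A patient who took every planned dose looks under-dosed. Cytarabine given in full in that cycle is affected in the same way.

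This matters for reading the exposure tables. Protocol 2.3 justifies the longer dosing schedule by a relationship between dose intensity and efficacy, and the trial stopped for futility, so readers will ask whether patients received the intended dose. The SAP expects these patients: the notes to its Figure 2-1 have them entering post-consolidation after recovery from HSCT, and 8.3.6.1 summarises MRD before and after HSCT for those who re-enter.

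**Working it through.** The plan gives no RDI figure for transplanted patients, so there is nothing to reproduce. The SAP formulas were applied directly.

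**Inputs**
- Planned midostaurin/placebo dose, 50 mg twice daily (Protocol 6.1.1.1, Table 6-1). Consolidation, Day 4 to the morning of Day 27: 23 × 100 + 50 = 2350 mg. Induction 1, from Day 8: 19 × 100 + 50 = 1950 mg. Post-consolidation: 28 × 100 = 2800 mg per cycle.
- Drug-free gap beyond Day 28: 30 to 100 days after transplant (Protocol 4.2.2) plus conditioning. Conditioning length is not given; 0 to 7 days is assumed.
- PDI: assumed to be planned dose/28, so 2350/28 = 83.9 mg/day for consolidation. Check: without HSCT a compliant cycle gives (2350/28)/83.9 = 100%.

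**Pre-HSCT cycle of 28 planned days.** Length L = 28 + gap, DI = 2350/L, and RDI reduces to 28/L.

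| Gap (days) | L | DI (mg/day) | RDI |
|---|---|---|---|
| 30 | 58 | 40.5 | 48.3% |
| 100 | 128 | 18.4 | 21.9% |
| 107 | 135 | 17.4 | 20.7% |

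The ratio is the same if HSCT follows a 28-day induction cycle. With PDI = 100 mg/day the range is 40.5% to 17.4%, but a compliant cycle without HSCT would then show only 83.9%.

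**Cycle prolonged for count recovery, dosing continued.** Doses are 3050, 3750 and 4450 mg for 35, 42 and 49 days. With a gap of 31 to 38 days, and PDI based on either 28 days or the cycle's own length, RDI is 48–55%, 53–61% and 56–66%: roughly 50–66% overall. With a gap of 100 to 107 days it is 25–36%.

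**Consolidation phase**, the level at which SAP 6.7.3.2 tabulates the RDI bands. With k cycles of 28 days, RDI = 28k/(28k + gap). For gaps of 31 to 107 days:
- k = 1: 47.5% to 20.7%
- k = 2: 64.4% to 34.4%
- k = 3: 73.0% to 44.0%
- k = 4: 78.3% to 51.1%

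**Whole study.** Induction 1, one consolidation cycle, a 100-day gap, then post-consolidation, with every cycle taken as 28 days:
- 3 post-consolidation cycles: 12700/140 = 90.7 mg/day becomes 12700/240 = 52.9, RDI 58.3%
- 6 cycles: 21100/224 = 94.2 becomes 21100/324 = 65.1, RDI 69.1%
- 12 cycles: 37900/392 = 96.7 becomes 37900/492 = 77.0, RDI 79.7%

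**Duration (SAP 6.3).** The gap is added in full. In the 3-cycle scenario, 21 + 28 + 84 = 133 days (19.0 weeks) becomes 165 days (23.6 weeks) with a 32-day gap, in the same 12–24 week band, or 233 days (33.3 weeks) with a 100-day gap, one band higher. With 6 cycles, 217 days (31.0 weeks) becomes 249 or 317 days (35.6 or 45.3 weeks), still within 24–48 weeks. With 12 cycles, 385 days (55.0 weeks) is already in the top band.

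**The case against.** The best reply is that dose per calendar day is a legitimate measure of drug delivered, and a transplant gap does reduce it. Last-minus-first duration is a common convention: it counts every interruption and matches the continuous on-treatment window of SAP 3.6.2. Interruptions with reasons, dose listings, cumulative dose and HSCT by phase are also reported, so a careful reader could find the gaps. The visit panel might record HSCT in a way that closes the cycle, PDI might be defined to absorb the gap, or the original SAP, to which Section 12 refers for appendices, might deal with it.

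The point about convention stands for duration, which is the weaker part. The possible rescues are not in the documents. Even if HSCT were recorded as a cycle of its own, 6.7.3.1 sums all cycle lengths, so whole-study DI would not change. A PDI that absorbed the gap could cancel the RDI effect, but DI would remain low, and 6.7.1 points the other way. Listings do not correct the RDI tables.

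Numbers may be small. No patient had been enrolled at Amendment 1 (08-Jun-2018), and the study stopped on 23-Sep-2019, 472 days later, with most patients discontinuing within weeks. The 12-cycle scenario needs 28 + 28 + 100 + 336 = 492 days, so it could arise only in patients who continued after the stop.

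A reader might infer that the artefact creates or hides a difference between arms. HSCT does occur after randomization, so this is possible, but the documents give no HSCT rate by arm.

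**Conclusion.** The point holds for transplanted patients who resume study drug. For a fully dosed 28-day pre-HSCT cycle, reported RDI is about 48% down to 21%, assuming PDI = planned dose/28 and 0 to 7 days of conditioning. Phase-level and whole-study RDI are lowered less, as shown above. The number of patients affected is unknown.

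Three stronger readings are not supported.
- Not every compliant transplanted patient falls below 50%. Those who never resume come under the last-cycle rule, prolonged cycles with a short gap reach roughly 50–66%, and the banded tables are by phase, where four consolidation cycles give 78% to 51%.
- A general shift of duration bands is not shown. Only one of the six scenarios moves, and by one band.
- The efficacy conclusion is not in question. EFS, OS and the futility decision do not use DI, RDI or exposure duration. The effect is confined to descriptive exposure and compliance tables.

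**What to change.** In SAP 6.2, close the last pre-HSCT cycle at its planned or recovery length (28 days, or up to 42 or 49), or earlier if the transplant procedure begins sooner. In 6.7.2 and 6.7.3, exclude from the denominators the time from that cycle end to the first post-HSCT dose of study drug, using recorded dosing and HSCT dates. The compliant 28-day cycle then returns to (2350/28)/83.9 = 100%. State PDI in mg/day, since every RDI depends on it.

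In 6.3 and 6.5, last-minus-first duration can stay, but report duration excluding the HSCT interval beside it. Summarise the length of the HSCT gap by arm.

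Protocol 7.1.3 has HSCT patients entering post-consolidation within 48 hours after the consolidation phase ends. This must be reconciled with the 30–100 day window in 4.2.2 and 4.2.3, because it bears on where the cycle and phase boundaries fall.

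The cost is a SAP wording change and one derivation. HSCT timing is already needed for SAP 8.3.6.1 and 8.3.9. The documents name no field for the start of conditioning, so the rule should not depend on one. The downside is that RDI is no longer a simple calendar ratio for transplanted patients.

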6.3 Duration of exposure to Midostaurin/placebo

Duration of exposure to a study component (days) = (last date of last intake to the study component) – (date of first administration of the study component) + 1;

6.4 Duration of exposure to cytarabine, daunorubicin or Idarubicin in induction and consolidation treatment phases

For each treatment cycle, duration of exposure to the study treatment components (days) = (last date of last intake to the study component) – (date of first administration of the study component) + 1;

Therefore, the total duration of exposure will be the sum of exposures for each treatment cycles in induction and consolidation.

6.5 Duration of exposure to study treatment

Duration of exposure to study treatment is considered by taking into account the duration of exposure to Midostaurin/Placebo, Daunorubicin (or Idarubicin) and Cytarabine:

Duration of exposure to study treatment (days) = (last date of exposure to study treatment) – (date of first administration of study treatment) + 1;

The last date of exposure to study treatment is the latest of the last dates of exposure to Midostaurin/Placebo, Daunorubicin (or Idarubicin) and Cytarabine.

6.6 Cumulative dose

Cumulative dose of a study treatment component is defined as the total dose given during the study treatment exposure and will be summarized for each of the study treatment components. The **actual cumulative dose** refers to the total actual dose administered, over the duration for which the patient is on the study treatment as documented in the Dose Administration eCRF. Cumulative dose for Midostaurin/Placebo is presented in mg. Daunorubicin or (Idarubicin) and Cytarabine is subcutaneously administered and dose administered is collected in mg/m².

For patients who did not take any drug the actual cumulative dose is by definition equal to zero.

The **planned cumulative dose** for a study treatment component refers to the total planned dose as per the protocol in the duration of exposure to study treatment.

6.7 Planned dose intensity (PDI), Dose intensity (DI) and relative dose intensity (RDI) by cycle

6.7.1 Planned cycles lengths

A cycle length is planned to be 28 days for all patients who reached CR, CRi with adequate blood count recovery, PR or No response at end of each cycle. If the patient has CRi without adequate blood count recovery, the planned cycle length might be prolonged to:

- Up 42 days for induction cycle 1
- Up 49 days for induction cycle 2
- Up 49 days for all consolidation and post-consolidation treatment cycles.

6.7.2 Dose Intensity (DI) by cycle analysis

6.7.2.1 Midostaurin/Placebo

For cycles except last cycle or last cycle with length as scheduled or longer

- DI_c [mg/day] = (Total actual dose in an actual cycle [mg]) / actual cycle length [days]

For all cycles

- RDI_c [%] = DI_c [mg/day] / Planned Dose Intensity [mg/day] * 100

6.7.2.2 Cytarabine, daunorubicin or Idarubicin

The same rules will be applicable as above with the unit of mg/m².

6.7.3 Dose Intensity (DI) over study period

6.7.3.1 Midostaurin / Placebo

Dose intensity (DI) for patients with non-zero duration of exposure is defined as follows:

$$DI \text{ (mg/day)} = \frac{\text{cumulative dose}}{\sum_{i=1}^k (\text{actual cycle lengths})_i}$$

and $i = 1, 2, 3, \dots, k$ are the indices for the cycle.

For patients who did not take any drug the DI is by definition equal to zero.

Relative dose intensity (RDI) is defined as follows:

$$RDI \text{ [%]} = DI \text{ [mg/day]} / \text{Planned Dose Intensity [mg/day]} * 100$$

6.7.3.2 Cytarabine, daunorubicin or Idarubicin

The same rules will be applicable as above with the unit of mg/m².

Frequencies for RDI will be produced by treatment group, study treatment component and treatment phase for the following categories:

- 0 to < 50%
- 50 to < 70%

- 70 to < 90%
- 90 to < 110%
- $\geq 110\%$

6.8 Dose reductions, interruptions or permanent discontinuations

‘Dose changed’, ‘Dose interrupted’, and ‘Dose permanently discontinued’ fields from the exposure eCRF pages will be used to determine the dose reductions, dose interruptions, and permanent discontinuations, respectively.

The corresponding fields ‘Reason for dose change/dose interrupted’ and ‘Reason for permanent discontinuation’ will be used to summarize the reasons.

A dose change is either ‘change in prescribed dose level’ or ‘dosing error’ where actual dose administered is different from the prescribed dose.

For the purpose of summarizing interruptions and reasons, in case multiple entries for interruption that are entered on consecutive days with different reasons will be counted as separate interruptions. However, if the reason is the same in this block of entries, then it will be counted as one interruption.

Reduction: A dose reduction is, where the prescribed dose level is lower than the previous prescribed dose level or where the actual dose administered is lower than the calculated dose amount based on the prescribed dose. Therefore any dose change to correct a dosing error will not be considered a dose reduction. Only dose change is collected in the CRF, number of reductions will be derived programmatically based on the change and the direction of the change. In addition, if a patient moves to a less frequent regimen, such changes will then be counted as dose reductions.

7 Analysis of the primary objective

The primary objective of this study was to determine if the addition of midostaurin to standard induction and consolidation therapy, followed by single agent post-consolidation therapy improves event-free survival (EFS) in patients with newly diagnosed FLT3-WT AML.

As the study concluded at the first efficacy interim analysis due to futility, the endpoints will be derived and summarized based on the final data, but no testing (p-values) will be provided in the final CSR.

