6.1.1 Dosing regimen

[figure not shown]
On Day 1 of study treatment, the first dose of induction chemotherapy will be administered.

Daunorubicin/ idarubicin and cytarabine are approved drugs and will be sourced either according to local practice or centrally. Please refer to the Package Insert for complete guidelines for administration and for safety monitoring guidelines.

The dosage of daunorubicin/idarubicin and cytarabine will be adjusted based on body surface area (BSA) calculated before administration. To calculate BSA, the height at baseline and weight on the first day of the respective treatment cycle will be used.

Dose modification for obese patients:

There is no clearly documented adverse impact of treatment of obese patients when dosing is performed according to actual body weight. Therefore, all dosing is to be determined solely by the patient’s BSA as calculated from actual weight. This will eliminate the risk of calculation error and the possible introduction of variability in dose administration.

6.1.1.1 Treatment regimen:

First Induction:

- **Cytarabine** 200 mg/m²/day will be administered by continuous intravenous infusion (CIVI) on Days 1-7 (168 hour infusion).
- **Daunorubicin** 60 mg/m²/day *or* **idarubicin** 12 mg/m²/day will be administered intravenously by IV push (IVP) or short (30 minutes) infusion on Day 1-3.
- **Study drug (midostaurin** 50 mg [two 25 mg capsules] **or placebo** [2 capsules]) will be administered twice per day by mouth from Day 8 until 48 hrs prior to the start of next cycle (i.e. the morning of Day 27 if hematopoiesis recovers timely (cycle length of 28 days) or later if the cycle needs to be prolonged for blood count recovery). Patients should take their doses at approximately the same time each day, and approximately 12 hours should elapse between the morning and evening doses. On days that PK samples are obtained, the patient should take study drug during the clinic visit after the pre-dose PK sample and prior to post-dose PK samples, when instructed by the study staff. Each daily dose should be given with food and a glass of water (~240 mL). Patients should be instructed to swallow capsules whole and not chew capsules. If vomiting occurs, no re-dosing is allowed prior to the next scheduled dose. The soft capsules should be removed from the blister pack only shortly prior to administration. The capsules may have an unpleasant odor, which disappears a few seconds after the blister foil is opened.

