A bone marrow aspiration will be performed in all patients between Day 21-28 to determine the need for a second induction cycle. If the bone marrow aspirate is insufficient to make a determination of remission, then the bone marrow assessment should be repeated after about one week.

A disease assessment will be performed at the end of induction 1 based on bone marrow and peripheral blood assessments. If the response is CR or CRi with adequate blood recovery the patient will proceed to the consolidation phase. If the response is CRi without adequate blood count recovery, the patient will continue to be treated with Midostaurin/Placebo and observed up to 2 weeks to get the platelet $\geq 50 \times 10^9/L$ and neutrophil $\geq 1 \times 10^9/L$ (i.e., adequate blood count recovery) to be able to move to consolidation. In such cases a response assessment will be performed at day 42 (28 days plus the time window of 2 weeks for adequate blood count recovery)

If patients after induction 1 therapy still show $\geq 5\%$ blasts (i.e., no CR or CRi) in their D21-D28 bone marrow, then they require a second induction treatment. Dosing of midostaurin/placebo should be stopped immediately after knowledge of $\geq 5\%$ blasts persistence. 48 hours thereafter the second induction treatment should start.

Of note, Physicians should consider earlier bone marrow exams in patients whose peripheral blood counts are not recovering or recovering in an unexpectedly slow manner.

Second Induction:

Patients who still have more than $\geq 5\%$ blasts in their bone marrow (no CR or CRi) after induction cycle 1 require a second induction treatment. Dosing of midostaurin/placebo should be stopped immediately. 48 hours thereafter the second induction treatment should start.

- **Intermediate-dose cytarabine (IDAC)** 1500 mg/m² will be administered by intravenous infusion over 3 hours every 12 hours on Day 1 to 3. Serial neurologic evaluations will be performed before and following the infusion of intermediate-dose cytarabine. **For patients of age 60 years or older at the time of study entry a dose of 1000 mg/m² will be administered.**
- **Daunorubicin** 50 mg/m²/day *or* **idarubicin** 10 mg/m²/day will be administered intravenously by IV push (IVP) or short (30 minute) infusion on Day 1-3 **for patients <60 years only. Patients ≥ 60 years at the time of study entry will not be given daunorubicin *or* idarubicin**

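### Read literally, SAP 6.8 classes the protocol-scheduled Induction 2 anthracycline step-down in patients under 60 as a dose reduction

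*SAP*

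**What the plan says.** SAP 6.8 takes its data from the eCRF items for changed, interrupted and permanently discontinued doses. It says these "fields from the exposure eCRF pages will be used to determine the dose reductions, dose interruptions, and permanent discontinuations, respectively". Its definition of a change is: "A dose change is either ‘change in prescribed dose level’ or ‘dosing error’ where actual dose administered is different from the prescribed dose".

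A reduction then has two limbs. The first is "A dose reduction is, where the prescribed dose level is lower than the previous prescribed dose level". The second is an administered dose below the amount calculated from the prescribed dose. The count is made by program: "number of reductions will be derived programmatically based on the change and the direction of the change". The only exclusion stated is a change made to correct a dosing error. SAP 6.1 reports the number and percentage of patients "who have dose reductions or interruptions, and the reasons, will be summarized by treatment group", on the safety set.

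Protocol 6.1.1 and Table 6-1 schedule two different anthracycline doses in induction:

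- **Induction 1, all ages:** daunorubicin 60 mg/m²/day, or idarubicin "12 mg/m²/day will be administered intravenously by IV push (IVP) or short (30 minutes) infusion on Day 1-3".
- **Induction 2, patients under 60 only:** daunorubicin 50 mg/m²/day, or idarubicin "10 mg/m²/day will be administered intravenously by IV push (IVP) or short (30 minute) infusion on Day 1-3". Patients aged 60 or over receive no anthracycline in this cycle.

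**The concern.** The reference for a reduction in SAP 6.8 is the dose the patient had before, not the dose the protocol plans for the current cycle. The two differ wherever the protocol itself lowers a dose between cycles, as it does for the anthracycline in patients under 60.

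Induction 2 is given to patients without an adequate response to Induction 1 (Protocol 4.2.1). A patient treated at the full scheduled dose in both cycles would then enter the reduction table because Induction 1 did not produce an adequate remission, not because a dose was cut. A by-arm table meant to describe how chemotherapy was modified would partly describe how often each arm needed a second induction.

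The SAP would also use two yardsticks. Planned cumulative dose (SAP 6.6) is defined by the protocol, and relative dose intensity (SAP 6.7) divides by planned dose intensity. The same patient could be at 100% of plan there and dose-reduced under 6.8.

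**Working it through.** The plan states no figure on this point, so there is none to reproduce. The check applies the first limb of SAP 6.8 to the protocol's doses and compares the result with the planned dose for the same cycle.

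**Inputs (mg/m²/day)**

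- Daunorubicin plan: Induction 1 = 60, Induction 2 = 50 (Protocol 6.1.1, Table 6-1).
- Idarubicin plan: Induction 1 = 12, Induction 2 = 10 (same source).
- Bilirubin-based daunorubicin levels: 100%, 75% or 50% of dose (Protocol Table 6-2). That is 60, 45 or 30 in Induction 1 and 50, 37.5 or 25 in Induction 2.

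**Step 1: the scheduled step.** Relative fall = 1 − (Induction 2 dose / Induction 1 dose).

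- Daunorubicin: 1 − 50/60 = 0.167, or 16.7%.
- Idarubicin: 1 − 10/12 = 0.167, or 16.7%.

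Both are below the preceding level, so the first limb is met. Against the Induction 2 plan the same doses are 50/50 = 100% and 10/10 = 100%.

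**Step 2: all daunorubicin combinations.** This assumes that the reduced dose is entered as the prescribed dose, so that the second limb does not apply.

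| Induction 1 → Induction 2 | Lower than preceding dose (SAP 6.8) | Below Induction 2 plan |
|---|---|---|
| 60 → 50 | yes | **no** |
| 60 → 37.5 | yes | yes |
| 60 → 25 | yes | yes |
| 45 → 50 | no | no |
| 45 → 37.5 | yes | yes |
| 45 → 25 | yes | yes |
| 30 → 50 | no | no |
| 30 → 37.5 | **no** | yes |
| 30 → 25 | yes | yes |

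The two criteria disagree in two rows. 60 → 50 is a false count. 30 → 37.5 is a miss: it is a rise, but 37.5/50 = 75% of plan. In two further rows, 45 → 37.5 (75% of plan in both cycles) and 30 → 25 (50% in both), SAP 6.8 registers a step in Induction 2 although the patient's position relative to plan has not changed.

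**Step 3: size in the table.** For one arm, the share falsely counted is

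n × p × f × m / N,

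where N is the arm's safety set, n its patients under 60, p the proportion of those who receive Induction 2, f the proportion of these given full scheduled doses of the same anthracycline in both cycles, and m the proportion of such steps that sites mark as a dose change. The documents give none of n, p, f or m, so no percentage can be computed. Under 1:1 randomization stratified by age, n/N should be similar in the two arms, so an arm difference would come mainly through p.

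**The case against.** **The eCRF trigger.** A step enters the count only if the site marks a dose change. Protocol 6.3.1 uses that term for modifications made because a patient does not tolerate the schedule, and Protocol 6.6 lists prescribed dosages and dose changes as separate things to record. On that reading a full scheduled Induction 2 dose is not a change at all. This stands as a condition on the finding, because the eCRF completion rules are not in the documents. It does not remove the finding: SAP 6.8's own definition of a change includes any change in the prescribed level, and differing site practice would make the count depend on the site.

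**Not every patient.** A reader might infer that all patients under 60 who reach Induction 2 are counted. The table above shows otherwise: a patient cut to 45 or 30 in Induction 1 who then receives 50 has a rise. A switch between daunorubicin and idarubicin is not addressed.

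**Cytarabine.** SAP 6.8 adds that "if a patient moves to a less frequent regimen, such changes will then be counted as dose reductions", and a reader might extend the point to the move from a 7-day infusion to 3 days. The documents do not support that. Dosing goes from a continuous infusion of 200 × 7 = 1400 mg/m² per cycle to 12-hourly doses totalling 1500 × 2 × 3 = 9000 mg/m², or 1000 × 2 × 3 = 6000 mg/m² at age 60 or over. That is a shorter course, but not clearly a less frequent regimen and not a lower dose.

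**True reductions remain visible.** A reader might infer that real, toxicity-driven reductions are hidden. They are not. Reasons for change are summarized (SAP 6.1, 6.8), patient listings show doses with reasons (6.1), relative dose intensity is tabulated by component and phase (6.7.3.2), and adverse events requiring dose adjustment have their own summary (9.2). This stands. However, 6.8 uses the reason field only to summarize reasons, not to exclude scheduled steps from the count.

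**Small consequence.** The trial stopped for futility and the table is descriptive. This also stands.

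**Conclusion.** The point holds in limited form. As written, SAP 6.8 classes as dose-reduced a patient under 60 who receives the full Induction 1 anthracycline dose and then the scheduled Induction 2 dose of the same drug, a 16.7% step, if the site records it as a dose change. It can also leave uncounted a dose that is below plan (30 then 37.5), if the reduced doses are entered as the prescribed doses.

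The consequence is a potentially misleading chemotherapy dose-reduction summary by arm, in which false counts follow each arm's Induction 2 use among patients under 60. The number affected cannot be derived from the documents, and the effect is diluted in the whole safety set because patients aged 60 or over have no Induction 2 anthracycline.

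EFS, OS and relative dose intensity do not use this derivation. Midostaurin/placebo is planned at 50 mg twice daily in every phase, so there is no scheduled step to misclassify. It would therefore go too far to infer that one arm's study drug will appear less tolerable. The finding concerns counting only and takes no position on which dose is right.

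**What to change.** In SAP 6.8, state that:

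- a chemotherapy reduction is a prescribed or administered dose below the protocol-planned dose for that component, cycle and age group;
- protocol-scheduled changes between cycles or phases are not reductions, whether or not the site marked a dose change;
- a reduction carried forward at the same percentage of plan is counted once, so that a planned-dose comparator does not recount one sustained reduction in each later cycle.

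It would help to add how a partial return towards plan is counted (for example 50% then 75% of plan), and how a switch of anthracycline is handled.

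The cost is a short insertion in SAP 6.8 and one change to the derivation program. The planned doses by phase and age group are already in Protocol Table 6-1 and are needed for relative dose intensity in any case. No new data collection is required.
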